## 6.8 Treatment delivery and on-table adaptive replanning

All patients will receive radiation therapy using photons on the MRIdian Linac system for alignment, dose prediction, tracking, gating, and on-table adaptive planning when clinically indicated.

For each delivered fraction, a volumetric MRI data set will be obtained using system integrated sequences; the preferred sequence is a balanced gradient echo most similar to Siemens True FISP scan with T2\*/T1 weighted image-characteristics with at least a 1.5 x 1.5 x 3.0 mm image matrix resolution. The external contour of the patient should be inside the field of view where there are beam angles that will be used for treatment.

The target volume will be rigidly aligned to a reference position by virtual couch movement in cranio-caudal, left-right and anterior-posterior direction to optimally align with the planned treatment isocenter. Depending on operator assessment, these shifts are then executed, and treatment is initiated.

If optimal target to isocenter alignment cannot be achieved, system integrated deformable image registration between the primary treatment image data (used for simulation and treatment planning) and the respective fraction MRI dataset will be performed. Original plan contours are propagated onto the respective fraction MRI dataset. If on-table adaptive planning is clinically indicated, then all tumor volumes and

critical structures within 3 cm radially and 2 cm cranial-caudal from the surface of the PTV will be re-contoured as needed on the volumetric high-quality MRI data set.

An estimated delivered dose will be calculated and saved using the software on the console (dose prediction). An adapted radiation therapy plan is created based on physician assessment of medical necessity. General guidelines to establish medical necessity include but are not limited to the following:

- Any OAR constraint is violated. The same constraints used to develop the original plan will be used to on the day of treatment to determine the need to create an adapted plan.
- Reduction in GTV and/or PTV covered by the prescription isodose compared to the original plan.
- Favorable shift in the relation between GTV and dose-limiting OARs, such that adaptive planning would likely improve the coverage of the GTV.

For patients treated to multiple lesions, adaptive replanning may be required in order to ensure that cumulative dose to OARs meets constraints. As the original treatment plans are required to cumulatively meet all OAR constraints, adaptive replanning must be performed on the day of treatment delivery in order to achieve at least the same dose avoidance as the original plans.

Adaptive dose re-planning does not need to be performed if the dose prediction shows compliance with minimum dose coverage of the GTV and adherence to upper dose/volume limits of all OARs.

If multiple lesions are to be treated on this study, it is recommended that each one should be treated separately as treatment of multiple lesions may significantly prolong total treatment time, which may be poorly tolerated by the patient. However, treatment of multiple lesions on this trial during the same session is permitted if the treating physician believes that treatment would be completed within a feasible amount of time.

During radiation dose delivery, continuous cine MR image acquisition in at least one principal plane (suggested sagittal, but at the discretion of the treating physician) is mandatory for soft tissue tracking and radiation beam gating. To this end, a tracking slice of 7-10 mm thickness will be positioned to include a cross-sectional cut of the target for intra-fractional soft tissue tracking. The tracking/gating volume will be preferably delineated based on the GTV, or otherwise on a well visualized surrogate in proximity to the GTV.

The software should be set so that if 5% or more of the tracked target extends outside of the boundary the beam will gate off. For soft tissue tracking and gating, a minimum cine frame rate of 4 frames/second is mandatory throughout dose delivery although higher frame rates (e.g., 8 frames/second) may be used if available.

During study treatment, a time log will be used to record the following events, at a minimum:

- Patient enters the treatment room
- Volumetric scan initiated
- Target volume/OAR contouring started
- Target volume/OAR contouring ended
- Predicted dose calculation completed
- Treatment plan re-optimization finalized (if performed)
- Treatment delivery started
- Treatment delivery completed

#### 6.9 Treatment plan storage

All clinically approved plans, structures delineated for dose prediction, predicted doses, as well as all adapted radiation therapy plans will be saved and stored in the MRIdian associated software. All initial plans, structures delineated initially and on-table, predicted dose, and adapted plan data are to be backed up for permanent storage and potential later analysis.

#### 6.10 Additional radiation therapy

It is permissible for radiation therapy to be delivered to lesions other than those that are treated on this study. This could be to other lesions that are present at the time that SABR is delivered as part of this study, or new lesions that may appear after the completion of SABR on this study. However, additional radiation therapy should be avoided that would directly overlap or be in proximity to a lesion that previously received radiation therapy on this study that could significantly increase the risk of potentially severe toxicity. It is strongly recommended that additional radiation therapy not be delivered off study to lesions within the same organ or otherwise within 3 cm of a lesion treated on this study so that any toxicity related to study therapy can be accurately assessed. Otherwise, if it is medically necessary to deliver additional radiation therapy off study, especially if there are no reasonable treatment alternatives, and if the treating physician believes that the risk of severe toxicity is reasonably low and justified by the potential benefit of radiation therapy then it would be permissible to deliver additional radiation therapy regardless of location.

#### 6.11 Systemic therapy

There will not be any cytotoxic chemotherapy, targeted systemic agents, and/or investigational agent administered within 2 weeks prior to or following delivery of

radiation therapy on this study, provided that the patient does not have any ongoing grade 2 or higher toxicity from any prior treatment.

If a lesion is to be treated in the abdomen or pelvis, it is required that vascular endothelial growth factor (VEGF) inhibitors such as bevacizumab not be given at least 4 weeks prior to or after study therapy because of a potentially increased risk of GI toxicity.

Hormonal therapy or immunotherapy such as immune checkpoint inhibitors that had begun at least 4 weeks prior to SABR will be allowed, provided there are no grade 2 or higher toxicities ongoing as a result of such therapies.

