**Exclusion criteria:**

Patients will not be eligible for study entry if any of the following criteria are met:

1. Subject has contraindication to having an MRI scan
2. Subject has central or ultra-central lung tumor that would receive SABR on this study, defined as a lesion located within 2 cm of the trachea and proximal bronchial tree
3. Subject has received cytotoxic chemotherapy or investigational agent within 2 weeks of SBRT
4. Subject has uncontrolled brain metastases, spinal cord compression, or leptomeningeal carcinomatosis
5. Subject has any unresolved toxicity (Common Terminology Criteria for Adverse Events version 5.0 > grade 2) from previous anti-cancer therapy
6. Any condition, therapy or lab abnormality in the opinion of the investigator that would interfere with patient safety, evaluation of study treatment or interpretation of study results
7. Subject has received prior radiation therapy that directly overlaps any radiation therapy given in this study
8. Subject has received radiation therapy that could lead to an unacceptably high risk of clinically significant normal tissue injury due to high cumulative normal tissue dose as determined by the investigator
9. Female subject who are pregnant or breastfeeding
10. Subject who has received vascular endothelial growth factor (VEGF) inhibitor such as bevacizumab within 4 weeks prior to study therapy or planned to receive it within 4 weeks after study therapy.

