### 5. PATIENT SELECTION

#### 5.1 Inclusion criteria

1.  $\geq 18$  years of age at the time of study enrollment
2. Biopsy-confirmed primary or metastatic carcinoma with involvement of the lung, liver, adrenal gland, pancreas, kidney, and/or abdominal/pelvic lymph node that would receive SABR
3. Any lesion that would receive SABR is no larger than 5 cm in greatest dimension
4. 1-10 total lesions that would receive SABR
5. If multiple lesions are treated, they must be at least 3 cm apart
6. Eastern Cooperative Oncology Group (ECOG) performance status of 0-2
7. Life expectancy at least 6 months
8. Women of childbearing potential and men must agree to use adequate contraception (hormonal or barrier method of birth control) prior to study entry and for the duration of study participation. Abstinence is acceptable if preferred by patient. Should a woman become pregnant or suspect she is pregnant while participating in this study, she must inform her treating physician immediately.

9. Patients receiving hormonal therapy or immunotherapy such as immune checkpoint inhibitor that had begun at least 4 weeks prior to SABR will be allowed.

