## 5.2 Exclusion criteria

1. Contraindication to having an MRI scan
2. Central or ultra-central lung tumor that would receive SABR on this study, defined as a lesion located within 2 cm of the trachea and proximal bronchial tree
3. Cytotoxic chemotherapy or investigational agent within 2 weeks of SBRT
4. Presence of uncontrolled brain metastases, spinal cord compression, or leptomeningeal carcinomatosis
5. Any unresolved toxicity (Common Terminology Criteria for Adverse Events version 5.0 > grade 2) from previous anti-cancer therapy
6. Any condition, therapy or lab abnormality in the opinion of the investigator that would interfere with patient safety, evaluation of study treatment or interpretation of study results
7. Prior radiation therapy that directly overlaps any radiation therapy given in this study
8. Prior radiation therapy that could lead to an unacceptably high risk of clinically significant normal tissue injury due to high cumulative normal tissue dose as determined by the investigator
9. Female patients who are pregnant or breastfeeding.
10. Patients who have received vascular endothelial growth factor (VEGF) inhibitor such as bevacizumab within 4 weeks prior to study therapy or planned to receive it within 4 weeks after study therapy.

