#### 7.2 Screening and Enrollment Procedures

Subject eligibility for the study will be determined after the screening process. The site investigator or qualified designee will review all inclusion and exclusion criteria to ensure that the subject qualifies for the trial.

The screening package will be uploaded in the Oncore Subject Console or sent by email to theMCI Multi-site Program. The following documents should be included:

- Signed Informed Consent Form
- Signed HIPAA form
- Eligibility Form signed by the Investigator
- Copy of redacted screening laboratory tests results
- Copy of redacted pathology report confirming diagnosis
- Copy of redacted imaging report.

- RECIST 1.1 evaluation
- Additional relevant documents or communications confirming subject eligibility.

The MCI multi-site program designee will review the submitted documents in order to verify documentation of patient eligibility.

Upon confirmation of eligibility, the Coordinating Center will provide authorization to the site study team to register the subject in OnCore.

Subjects will be considered enrolled after they have given informed consent and passed eligibility criteria. The date of enrollment will be the date all eligibility criteria has been confirmed by the MCI Multi-site Program.

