## 8.2 During Study Therapy

The following will be assessed on each day of radiation therapy after treatment delivery:

- ECOG Performance Status
- Vital Signs
- Adverse Events / SAE
- Concomitant Medications
- Complete Study Time Log

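### Inclusion 9 allows concurrent hormonal therapy or immunotherapy without the toxicity condition in section 6.11, so a patient with ongoing grade 2 toxicity from it passes eligibility but falls outside 6.11

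*Combined protocol and SAP*

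**What the plan says.** Four parts of the combined protocol and SAP bear on this.

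- **Inclusion 9** (Protocol Summary and section 5.1, same wording): "Patients receiving hormonal therapy or immunotherapy such as immune checkpoint inhibitor that had begun at least 4 weeks prior to SABR will be allowed". There is no toxicity condition.
- **Exclusion 5** (section 5.2): "Any unresolved toxicity (Common Terminology Criteria for Adverse Events version 5.0 > grade 2) from previous anti-cancer therapy". The Protocol Summary sets the same threshold. It is the only graded toxicity criterion in the eligibility lists, and grade 2 passes it.
- **Section 6.11, last paragraph**: the same therapies with the same four-week limit, but only "provided there are no grade 2 or higher toxicities ongoing as a result of such therapies".
- **Section 7.2**: "The site investigator or qualified designee will review all inclusion and exclusion criteria to ensure that the subject qualifies for the trial". The coordinating program then verifies the eligibility documents. Section 6.11 is not named in that process.

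Two other texts are relevant. Exclusion 6 is a discretionary criterion: "Any condition, therapy or lab abnormality in the opinion of the investigator that would interfere with patient safety" is one of its grounds. The first sentence of 6.11 bans certain systemic agents around radiation and then adds "provided that the patient does not have any ongoing grade 2 or higher toxicity from any prior treatment".

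**The concern.** Two rules in one protocol give different answers for the same patient. Someone on a checkpoint inhibitor with ongoing grade 2 toxicity from it meets inclusion 9, is not caught by exclusion 5 and can be registered. Section 6.11 does not allow that patient to be on the drug with SABR. A site can follow section 5 exactly and still deviate from section 6.

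The treatment is a single fraction, so it cannot be adjusted once delivered. Section 8.2 places the listed treatment-day assessments after the beam: "The following will be assessed on each day of radiation therapy after treatment delivery". No assessment listed for that day would apply 6.11 beforehand. The eligibility criteria are the natural place for the condition, and it is missing there. With up to five sites, the conflict may also be resolved differently from one site to another.

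**Working it through.** This is a comparison of texts. The plan states no figure on this point, so there is none to reproduce.

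**Step 1. Apply each rule by CTCAE grade** of ongoing toxicity from concurrent hormonal therapy or immunotherapy started at least four weeks before SABR.

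| Grade | Inclusion 9 and exclusion 5 | Section 6.11 | Agree? |
|---|---|---|---|
| 0–1 | Passes | Allowed | Yes |
| 2 | Passes: inclusion 9 has no condition and exclusion 5 starts above grade 2 | Not allowed | No |
| 3 or higher | Fails exclusion 5 only if a therapy still being given counts as earlier anti-cancer treatment | Not allowed | Only on that reading |

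The certain conflict is at grade 2. If exclusion 5 covers only treatment already finished, the conflict extends to grade 3 and above.

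**Step 2. Look for text that closes the gap.** Exclusion 6 allows an investigator to turn an individual patient away, but it sets no grade 2 rule. Central verification in section 7.2 checks eligibility documents against the same criteria. Neither aligns the two rules.

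**Step 3. Look for an instruction on what to do.** Section 6.11 does not say whether such a patient should be excluded, taken off the drug or treated later.

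**Step 4. Possible frequency.** The documents give no prevalence, so the share *p* of enrolled patients in this position is an assumption, with patients taken as independent. Among 30 patients, the expected number is 30*p* and the chance of at least one is 1 − (1 − *p*)^30.

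- *p* = 1%: 30 × 0.01 = 0.3 expected; 1 − 0.99^30 = 0.26
- *p* = 5%: 30 × 0.05 = 1.5 expected; 1 − 0.95^30 = 0.79 (0.785)
- *p* = 10%: 30 × 0.10 = 3.0 expected; 1 − 0.90^30 = 0.96 (0.958)

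The range is wide and shows only that a case in a trial of 30 is plausible.

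**Step 5. Effect on the design figures.** The tolerability statements in section 13.4 are binomial probabilities of at most 4 events in 30. At a true rate of 10.5% this is 0.798 (stated as 80%), and at 21.4% it is 0.200 (stated as 20%). Their only inputs are 30, 4 and the assumed rate. The toxicity threshold for entry is not one of them, so these figures stand.

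**The case against.** The strongest reply is that both rules can be followed together. Inclusion 9 is a permission to enter. Section 6.11 belongs to the radiation therapy chapter and governs which systemic treatment may accompany SABR, and that chapter contains other conduct rules that the eligibility lists do not repeat. A site that reads the whole protocol would apply the narrower condition, perhaps by stopping the drug. It is true that 6.11 literally limits the therapy rather than enrollment. But the protocol never says to stop the drug, and inclusion 9 tells the site that the patient is allowed on it. The reply shows that a careful site could cope, not that the texts agree.

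Three stronger readings are tempting, and the documents do not support them.

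- *Screening is a scheduled adverse-event check that misses these patients.* The section 8.4 calendar has an adverse-event row at screening, but the section 8.1 list names only serious events, calendar footnote 5 restricts those to events related to protocol procedures or therapy, and section 11.1 starts adverse-event collection with treatment. Existing toxicity would more likely surface through history, examination, laboratory tests and concomitant medication, all of which section 8.1 does list.
- *The first sentence of 6.11 is a second eligibility limit that contradicts exclusion 5.* Its proviso is attached to a ban on drugs, and the meaning is unclear. It is wording to repair, not a rule that can be set against exclusion 5.
- *The stricter threshold is plainly the intended one.* Nothing shows which was meant. Relaxing 6.11 to above grade 2 would reconcile the texts as well.

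**Conclusion.** The conflict is real: wrong as written, and minor. For a patient with ongoing grade 2 toxicity from concurrent hormonal therapy or immunotherapy, the eligibility criteria say yes, 6.11 says no, and the protocol does not say how to proceed. The conclusion rests only on the wording of inclusion 9, exclusion 5, and sections 6.11 and 7.2. That it is confined to one grade assumes that ongoing therapy falls under exclusion 5; otherwise it is wider.

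A reader might infer that the mismatch distorts the tolerability result by admitting patients with existing toxicity. The documents do not show this. They give no prevalence and no link from grade 2 toxicity at entry to grade 3 or higher acute toxicity after SABR. The sample size, the limit of 4 in 30 and the section 13.4 probabilities are unaffected. Nor does every such patient necessarily get through, since exclusion 6 and ordinary clinical judgement may catch some.

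**What to change.** Choose one threshold and use it in inclusion 9, exclusion 5 and section 6.11.

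- **Preferred:** add to inclusion 9, in both the Protocol Summary and section 5.1, the condition "provided there are no grade 2 or higher toxicities ongoing as a result of such therapies", and bring exclusion 5 to grade 2 or higher in both places.
- **Alternative:** change 6.11 to toxicity above grade 2, leave the exclusion 5 threshold as it is, and state that therapy still being given counts under exclusion 5.

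With either choice, end the first sentence of 6.11 after the ban on agents around radiation. State the condition on toxicity from prior treatment as its own sentence, with the same threshold as exclusion 5. Add a line saying whether a patient who does not meet the 6.11 condition is excluded, stops the drug or has SABR delayed.

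The cost is a minor wording amendment with IRB review, and a change to the Eligibility Form if it repeats these criteria (its content is not in the documents). No new assessment, data field or analysis is needed. The preferred option may narrow eligibility slightly. For patients on concurrent therapy, 6.11 already implies this. Moving exclusion 5 to grade 2 would also reach patients with grade 2 toxicity from earlier treatment, and the sponsor should weigh that when choosing.

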#### 6.12 Additional local therapy

Surgery, percutaneous ablation, or other local therapy should not be planned to any lesion treated on this study at the time of patient enrolment. However, in the event of local tumor progression then such therapies may be considered.

### 7. STUDY PROCEDURES

#### 7.1 Informed Consent

Investigators or their authorized designees will be responsible for obtaining a signed informed consent form and authorization to use and disclose protected health information prior to conduct any study-specific procedures.

#### 7.2 Screening and Enrollment Procedures

Subject eligibility for the study will be determined after the screening process. The site investigator or qualified designee will review all inclusion and exclusion criteria to ensure that the subject qualifies for the trial.

The screening package will be uploaded in the Oncore Subject Console or sent by email to theMCI Multi-site Program. The following documents should be included:

- Signed Informed Consent Form
- Signed HIPAA form
- Eligibility Form signed by the Investigator
- Copy of redacted screening laboratory tests results
- Copy of redacted pathology report confirming diagnosis
- Copy of redacted imaging report.

- RECIST 1.1 evaluation
- Additional relevant documents or communications confirming subject eligibility.

The MCI multi-site program designee will review the submitted documents in order to verify documentation of patient eligibility.

Upon confirmation of eligibility, the Coordinating Center will provide authorization to the site study team to register the subject in OnCore.

Subjects will be considered enrolled after they have given informed consent and passed eligibility criteria. The date of enrollment will be the date all eligibility criteria has been confirmed by the MCI Multi-site Program.

## 8. PATIENT ASSESSMENTS

All evaluations should be completed as detailed below and per the study calendar in Section 8.4 of this protocol.

### 8.1 Screening assessments

All screening procedures must be done after the subject signs the informed consent. Assessments completed as part of the standard of care before patient signs the Informed Consent Form can be used for screening purposes as long as the test/procedure meets the protocol-required timelines. Note that source documents must identify the standard of care tests/procedures used for screening and must be reviewed by the investigator for clinical significance. Obtaining Informed Consent, FACT-G, RECIST 1.1 evaluation and confirming subject eligibility must be performed by a delegated study team member.

Screening assessments include:

- Signed informed consent
- Medical History and cancer history and therapy
- Physical Examination
- Vital signs (blood pressure, heart rate, temperature, oxygen saturation via pulse oximetry, weight)
- ECOG Performance Status
- Concomitant Medication
- Complete blood count (CBC) with differential and Comprehensive Metabolic Panel (CMP) Note: Laboratory tests must be reviewed and documented by the investigator or sub-investigator for clinical significance to confirm eligibility of the potential research subject.

- Imaging: CT scan of the chest, abdomen, and pelvis (IV and/or oral contrast as per physician discretion)
- RECIST measurements
- FACT-G survey
- Urine pregnancy test in women of childbearing potential (within 14 days of first day of study therapy)
- SAE
- Confirm Eligibility

